2.1.1 Cognitive Dysfunction (early and delayed) in Patients Undergoing CEA

Prior to surgery, patients are evaluated with an extensive battery of neuropsychometric tests (NPTs) that evaluate verbal memory, visuo-spatial organization, motor, and executive action. Patients are administered general anesthesia or regional anesthesia and clamps are applied to the common, internal, and external carotid arteries. The cerebral hemisphere ipsilateral to the surgical side generally receives collateral blood flow from the anterior and posterior communicating arteries, or less commonly from a shunt placed from the common to the internal carotid artery below and above the respective clamps. It is hypothesized that eCD occurs as a result of regional hypoperfusion as a result of insufficient collateral flow. Evidence for this comes from the fact that patients without EEG changes during cross clamping of the carotid artery but with decreased middle cerebral artery flow velocities as measured by transcranial Doppler are more likely to exhibit these deficits (14). After the repair of the carotid is complete, reperfusion is established and flow to the hemisphere is restored to either pre-operative levels or levels somewhat higher. Patients are then awakened, allowed to recover from the effects of anesthesia, and re-evaluated within 24h of the CEA with a different version of the same battery of NPTs to guard against practice effect. The different version of the same battery at the followup time points (baseline, 24 hours and at 30 days), also allows us to determine individual, rather than group differences/changes, in neuropsychometric performance.

To further control for practice effect, and ensure that neither anesthesia or perioperative pain are creating the false appearance of diminished cognition, we have used a surgical reference group of patients undergoing lumbar micro-discectomy or 1-2 level laminectomy lasting <4 hours, without blood transfusion or intensive care unit stay. Based on the difference scores for both the CEA and surgical reference patients, we calculate Z-scores. To the degree that patients in CEA group have “practice effect”, we expect the same “practice effect” in the surgical reference group

except they should not have cognitive changes from surgery. Therefore, negative changes in the neuropsychometric performance on these tests are recorded and normalized to the changes in neuropsychometric performance in the surgical reference group. Patients are labeled as either injured or not based on their Z-scores. We use rigorous cutoffs for injury that are associated with serum evidence of cerebral tissue injury and which predict mortality. Preliminary evidence suggests that eCD (24h) and dCD (30d) as defined by these criteria are due to regional cerebral ischemia rather than microembolization (15-17). In the randomized study proposed below, we will only include age, pre-op IQ and education-level matched patients for the reference surgical population who have been similarly screened for MCI pre-op (see below) and delirium postop (see below). Since perioperative pain is a wellrecognized confounder of NPT, albeit rare after CEA, we plan, *as we have done in all our prior work*, to exclude from analysis for all reference patients with pain scores > 4 on the 11-point Numeric Pain Intensity scale. Scores ≤ 4 will be recorded and analyzed in the univariate and multivariate models planned for the specific Aims. (18)

2.1.2 Statins & Cognition

The impact of statins on baseline cognition remains controversial. A study by Hajjar et al. concluded that statins are associated with better cognitive outcomes in elderly populations (19). Similarly, there is evidence statins may also improve cognition (20) through multiple mechanisms, including their action on eNOS (21). While some have suggested that statins may have a deleterious effect on cognition (22, 23), one large literature review suggests otherwise (24), concluding that no significant cognitive impairment can be concluded. A review by Golomb et al. addresses many of the issues related to the deleterious effects of statin and specifically simvastatin therapy (25, 26). The PROSPER study was an observational study in which 5,804 were evaluated at six different time points using four neuropsychological performance tests (27). They concluded that there was neither benefit nor detriment to the cognition of patients on pravastatin. However, the jury is still out on whether the adverse effects are significant for a large percentage of patients or are just rare occurrences. Whatever the case, our previous work strongly suggests that simvastatin is more neuroprotective than atorvastatin in CEA patients (13). While we do not have sufficient numbers of patients to comment on the comparative efficacy of less commonly prescribed statins, it appears that the lipophilic and small molecule size of simvastatin, may make it more effective at penetrating the blood brain barrier than atorvastatin, which although lipophilic, is significantly larger. We have also identified two important demographic factors which independently increase the risk of eCD: age >75 years, and diabetes mellitus (28). Genetic polymorphisms may also confer increased risk with the possession of the ApoE-ε4 (29, 30) allele being the best characterized, but complement cascade (13), phosphodiesterase (31) polymorphisms perhaps playing a role as well. The consequences of eCD after CEA is significant, with a higher risk of early mortality, with statins appearing to attenuate this difference in mortality (2).

2.1.3 Statin Ischemic Neuroprotection in Humans: Case for Differential Protection

Statins have revolutionized the treatment of hypercholesterolemia and its consequences of stroke and coronary artery disease. Endres has reviewed the effect of statin administration on

the incidence of stroke (32). Surprisingly, while large clinical studies have demonstrated a reduction in the incidence of cerebrovascular events, hypercholesterolemia by itself is not an established risk factor for stroke (32). It is thought that the action of statins is through noncholesterol lowering pleiotropic effects (32-34). Treatment at stroke onset may be beneficial as well. A large meta-analysis which included 113,148 patients found that statin therapy at stroke onset improves functional outcome at 90 days (35). Statins (rosuvastatin and atorvastatin) have been shown to reduce infarct volume and improve functional outcome in murine focal ischemia reperfusion models (36), in part by upregulating eNOS (21, 34). While several statins have been shown to be neuroprotective (including simvastatin, atorvastatin, and rosuvastatin), comparative studies looking at the relative protection achieved with doses equivalent to low, medium and high doses in humans do not exist (34, 37). There are studies in humans, which have shown that statins not only reduce the risk of stroke, but their use is associated with better stroke outcomes. Yet there is no data on whether any individual statin at any particular dose is likely to be more neuroprotective (38, 39). Our data in asymptomatic CEA suggests that eCD is rare in patients taking simvastatin or pravastatin at any dose, rare in patients taking high dose (80mg) atorvastatin or high dose (20mg) lovastatin and quite substantial in patients taking low dose lovastatin (<20mg), low dose atorvastatin (<80mg) or rosuvastatin at any dose. Overall, <50% of statin users are taking what appears to be a neuroprotective dose.

2.1.4 Cognitive Decline After Stroke: Inflammatory Biomarkers and Hippocampal Volume

The purpose of this study is to evaluate the safety, feasibility and outcome of administering three different statins at submaximal and maximal dose on eCD and dCD. However, we think that one potential mechanism of protection may be attenuation of systemic inflammatory state by statin therapy. For that reason we propose to look at measures of acute and chronic inflammation as demonstrated in a recent study of first ever strokes by Kliper et al. (40). They found that post-stroke elevations in “erythrocyte sedimentation rate (ESR) remained unchanged in follow-up examinations, suggesting a chronic inflammatory background in some patients and that higher levels of ESR were associated with worse performance in cognitive tests, particularly memory scores, even after adjustment for confounders. Moreover, in a multivariate regression model, higher ESR values were related to reduced hippocampal volume, suggesting that chronic post-ischemic inflammation may contribute to cognitive impairment and that statin regimes that are most effective in addressing this may promote hippocampal health and neuropsychometric memory performance. In the present study, we plan to monitor chronic and acute inflammation in study patients using serum ESR and CRP levels along with the lipid levels at designated time points and correlate them with NPT performance as a secondary aim.

[figure not shown]
2.1.5 Delirium and Mild Cognitive Impairment as Confounders

Both pre-operative mild cognitive impairment (MCI), and post-operative delirium may be confounders in studies of per-procedural cognitive injury. Mild cognitive impairment (MCI) has been defined as “mental impairment beyond what is felt to be normal for age.”(41). There are non-amnestic as well as amnestic subtypes of MCI with impaired memory being a prominent component for some and executive function a prominent symptom for others(41, 42). The

Minimental state examination (MMSE), the Montreal Cognitive Assessment (MoCA) and the EightItem Informant Interview to Differentiate Aging and Dementia (AD8) have been used to screen for MCI (including eCD, dCD) (43,44, 69, 70, 72). However, since the MoCA has been found to be a more adequate tool than the MMSE to screen for mild cognitive impairment (75), we will use the MoCA and the AD8 to screen for MCI at baseline. We will identify patients with both subtypes of MCI (44). While the incidence of pre-operative MCI may be as high as 50% in our patient population(45), the effect of MCI on postoperative cognitive dysfunction, at least following analogous studies of on-pump coronary surgery seems very small (46). Nevertheless, we will screen patients for cognitive decline ($AD8 \geq 2$) and the MoCA (≤ 25) prior to randomization.

Delirium is a syndrome consisting of a number of symptoms including an acute fluctuating disturbance in consciousness/attention, a change in cognition (memory deficit, disorientation, language disturbance), and a disruption in sleep-wake cycle. A considerable number of predisposing factors have been identified including: older age, cognitive impairment, cardiac failure, cerebrovascular disease, depression, sensory impairment, dehydration, malnutrition, and drug/alcohol dependence. Delirium can also be precipitated by metabolic disarray, medications, infection, and stress. While the incidence of delirium in patients undergoing some highly invasive vascular surgical procedures can be as high as 15%, the incidence in patients undergoing less invasive procedures such as asymptomatic carotid endarterectomy, appears to be no greater than 1.5%(47). Nevertheless, while less common than MCI, delirium, if present, can severely impact assessment of acute cognitive injury like eCD. Thus we will use the Confusion Assessment Method (CAM) to screen for it (48) in all CEA patients as well as all spine surgery controls, both at 24h and 30d. This instrument has been validated for use by nonpsychiatrists and can be performed in 5 minutes with high reliability. Nine questions are quickly addressed and if the patient has inattention (feature 2) that is acute in onset or fluctuating (feature 1) and either disorganized thinking (feature 3) or altered level of consciousness (feature 4) they will be considered delirious. Patients with delirium at any time point or MCI at study onset will be identified using the criteria outlined above, and these data will be analyzed in the univariate and multivariate models planned for the specific Aims.

Our preliminary data suggest the novel finding that cognitive performance can be used to identify a subtle form of cerebral injury, eCD and/or dCD with important clinical implications. Preventing this subtle injury with statins is a novel use of this class of drugs and identifying optimal dosing parameters and agents that are most protective, perhaps due to their lipophilicity/blood-brain barrier permeability, is equally unparalleled. The cerebral protective action of statins may be: 1) dose-, 2) time-, and 3) lipophilicity/blood barrier permeabilitydependent. It is unclear how long it is necessary to be on statin therapy for statins to be efficacious. However, the lipid lowering action of statins may be separate from the effect of statins to reduce eCD and dCD. This difference may be similar to the action of statins to reduce cardiac ischemia associated with percutaneous coronary intervention (PCI). As an example, a number of studies have demonstrated a reduction in peri-procedural non-Q-wave myocardial infarction in patients undergoing percutaneous coronary intervention (PCI) who were treated with a statin.(49-54) (59-54) Figure 1 shows the variability of these actions.(53)

[figure not shown]
One study looked at different statins -- atorvastatin (29% of cases), pravastatin (29% of cases), simvastatin (39% of cases), and fluvastatin (3% of cases) – administered for a little as 3 days prior to PCI. (50) The protective action of these statins occurs prior to the lipid lowering action of these statins. Their actions may be as anti-inflammatory or anti-thrombotic, which are not associated with changes in lipid profiles. Because of this separation in time between functional and biochemical actions of statins, statin action may be separated in time between when a statin may be neuroprotective and when a statin changes the lipid profile.

This aspect of statin neuroprotection has never been explored in detail in humans. Less lipophilic statins than simvastatin may become effective at high concentrations, underscoring the importance of generating a putative dose-response curve. While about 90% of patients at Columbia University Medical Center are already on a statin, we have reason to believe that in more underserved (lower income, less educated) populations, such as those at Montefiore Medical Center in Bronx NY and the University of New York in Buffalo NY, a smaller percentage of patients will be on statins prior to enrollment, and those that are likely to be on diminished doses that preliminary data suggests are less neuroprotective (55). Thus, if we can demonstrate a benefit in the total population, we may also have identified a pre-op therapy that would be particularly important for underserved populations. A second potentially innovative aspect of the proposal concerns the surveillance of systemic inflammation in this population. If certain statin regimes protect against eCD and dCD, whether these regimes are associated with less (or marked changes in) systemic inflammation will be important mechanistic data regardless of the result.

Our previous grant (R01 AG17604) was funded from July 1, 2003 to June 30, 2013. Over the 10 years the grant was funded, and the 15 years we have been studying patients having treatment for CEA, there has been a dramatic change in the incidence of eCD. We have investigated the reason(s) for this change. This analysis has been the primary outcome of this funding period. During our previous R01 grants, we enrolled 878 patients: 620 having CEA, 68 having CAS, and 190 reference patients having either “simple” spine surgery (155 patients) or coronary artery angiography or stenting (34). Of the 620 CEA patients, 559 had full neuropsychometric analysis completed pre- and post-operatively. Of these 559 patients, 231 were symptomatic patients undergoing CEA and 328 were asymptomatic. Symptomatic status refers to whether the patient

has a history of stroke or transient ischemic attack prior to surgery. We significantly surpassed our enrollment goals for all granting periods. All of the neuropsychometric data were analyzed, except for the data from 8 symptomatic and 4 asymptomatic patients because they experienced a peri-operative stroke. We utilized our reference population to account for practice effect and learning due to repeated neuropsychometric testing.

Performance was compared between patients having CEA and a reference group consisting of patients having “simple” spine surgery by testing them before, and 24h and 30 days after

[figure not shown]

surgery (11, 12). We generated Z-scores based on the mean and standard deviation of the change scores of reference group before and after surgery within 24h and at 30 days. We subtracted the mean change scores from the reference patients from the change scores for patients having CEA and divided this difference by the standard deviation of the change scores of the reference patients to generate Z-scores for each test, for each patient. Similar to previous studies (56), the tests were grouped by

cognitive domain and patients were considered to have postoperative eCD based on two criteria to account for both focal and global/ hemispheric deficits: (a) ≥ 2 SD worse than reference group in two or more cognitive domains or (b) ≥ 1.5 SD worse than the reference group in all cognitive domains tested.

We observed that the incidence of eCD has declined from 24.2% (1995-2000) to 12.0% (2007-2012) (Figure 4). We verified that the decrease in the incidence of eCD was not due to changes in patient characteristics by evaluating all of the common characteristics (age, gender, BMI, years of education, hypertension, diabetes mellitus, history of smoking, duration of cross-clamp, etc.), different surgeons (eight different surgeons provided care, 75.3% of the surgeries were performed by 3 surgeons), one anesthesiologist ([name]) was involved in ~75% of the cases, and the 12 different clinical coordinators were all trained by the same neuropsychologist ([name]). The surgical technique, anesthetic management, and indications for CEA have remained constant at this institution, as previously described (11, 12, 15). The only factor that changed over this time period was statin

use. Statin use increased from 34.2% to 88.7% (Figure 4). Of the 324 asymptomatic CEA patients with neuropsychometric testing, the pre-operative statin makeup was as follows: no statin (N=124), atorvastatin (N=94), simvastatin (N=66), fluvastatin (N=2), pravastatin (N=9), rosuvastatin (N=12), and lovastatin (N=17).

Although the incidence of peri-operative stroke was too low to comment on trends, asymptomatic patients taking statins had a significantly lower incidence of peri-operative stroke (0.0% vs. 3.1%, $P=0.02$) and exhibited significantly less eCD when taking statins (11.0% vs.

20.2%, $P=0.03$) than those not taking statins (2). Within the asymptomatic population, patients taking simvastatin exhibited significantly less eCD than those taking atorvastatin (3.0% vs. 16.0%, $P=0.005$) (Figure 5). There were no other significant pairwise differences in eCD among the other statin types (13). There were significant pairwise differences in HDL among statin types. HDL levels were higher in patients taking simvastatin compared to those taking atorvastatin ($P<0.001$). There were significant pairwise differences in LDL levels only between simvastatin and atorvastatin ($P=0.003$). However, there were no significant differences in triglycerides or total cholesterol levels among the statin types (13). Patients taking statins had significantly lower pre-operative monocyte counts than those not taking statins (7.0 ± 2.0 vs. $8.2\pm 2.1 \times 10^9/L$, $P<0.001$) at the time of surgery. However, there were no differences in monocyte counts amongst the statin types. The central question that we hope to answer is whether statin neuroprotection depends on the type of statin (simvastatin, atorvastatin or rosuvastatin and/or lipophilic versus non-lipophilic) or dose of statin.

A similar decrease in eCD was also seen in symptomatic and asymptomatic patients not taking and taking statins, and if looked at when both groups are analyzed together (symptomatic and asymptomatic patients together): $P=0.04$ (Asymptomatic), $P=0.19$ (Symptomatic), and $P=0.015$ (together).

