- *If subject is on 20 mg simvastatin + amlodipine – they will be in ARM 1 (observational) *If subject is on < 40 mg of simvastatin without amlodipine, they will be in ARM 2 and potentially randomized to 40 mg of simvastatin daily.
- *If subject is on < 20 mg of simvastatin + amlodipine, they will be in ARM 2 and potentially randomized ONLY to 20 mg of simvastatin daily not 40 mg.

All potential participants will be pre-screened for eligibility prior to offering them participation in the study. Once informed consent has been obtained, the final screening process to screen out those who may already have mild cognitive impairment (MCI) from the study will consist of the Montreal Cognitive Assessment (MoCA ≤ 25 = abnormal) and the Ascertain Dementia 8-item Informant Questionnaire (AD8 ≥ 2 = abnormal). If both assessments are not within normal ranges, these patients will not be randomized or assigned to the observational arm. Those with baseline MCI will be screened out from the study and not followed.

All of the potentially eligible subjects will be documented in the Study Screening Log (see Appendix III) and the logs will be collected monthly by the Central Coordinating Center at CUMC.

[figure not shown]
The randomization design is stratified by center, previous use of statin and in random blocks of 4 and 6. After the participant completes the screening process, ARM 2 and ARM 3 will be randomized using a centralized, secure web-based system created and managed by the Statistical Analysis Center (SAC) at the Mailman School of Public Health at Columbia University.

The study personnel will request the study drug from the site's Pharmacy/Research Pharmacy and provide the participant with the study drug instructions and corresponding amount of study drug capsules to take during their dosing period. The participants will self-administer the assigned daily doses of study statin and keep a Study Medication Compliance form (diary) of all doses taken, including their current statin doses, and the reasons for any missed dose(s) from enrollment to the day of their CEA. On the day of CEA, the remaining study drug capsules will be counted and the Study Drug Log will be collected to assess compliance.

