6.2.2 Screening Evaluation

The screening evaluations for MCI and hepatic and muscle testing will be completed after consent and prior to randomization in the study. The screening assessments must be completed prior to the subjects CEA such that the minimum of 2 doses (maximum of 18) are taken. The screening assessments are:

- MoCA
- AD8
- Laboratory (LFTs & CK)

All potential participants will be pre-screened for eligibility by reviewing patient chart and speaking with the patient regarding the inclusion/exclusion criteria prior to offering them participation and informed consent. The final screening process for participation will be after they have consented to participate in order to screen those who may already have mild cognitive impairment (MCI) from the study. The participants who provide informed consent will be screened for MCI by administering the MoCA (≤ 25 abnormal) and the AD8 questionnaire (≥ 2 abnormal). If both assessments are not within normal ranges, these patients will not be randomized or assigned to the observational arm. Those with baseline MCI will be screened out from the study and not followed.

- **MoCA (Montreal Cognitive Assessment):** The MoCA is a global cognitive screening test with favorable psychometric properties (69, 70); it has been shown to be more sensitive to executive impairment than the Mini-Mental State Examination (MMSE). (75) It screens 8 domains: visuospatial/executive, naming, memory, attention, language, abstraction, delayed recall, and orientation. The assessment takes approximately 10 minutes. The highest possible total score is 30 points, and the assessment is available in various languages, including Spanish.
- **AD8 (Eight-item Informant Interview to Differentiate Aging and Dementia):** A screening test in itself is insufficient to diagnose a dementing disorder. The AD8 is, however, quite sensitive to detecting early cognitive changes associated many common dementing illness including Alzheimer disease, vascular dementia, Lewy body dementia and frontotemporal dementia. (72) This will serve

as a preliminary screen for MCI by asking the patient if they have noted any memory loss in spite of having normal ADLs (65).

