9 STATISTICAL CONSIDERATIONS

9.1 General Design Issues

For all analyses, the primary outcome will be derived from changes in test scores between enrollment and the morning of surgery (baseline), Day 1 post CEA (12-25 h post-op) (eCD) and Day 30 +/- 5 days after CEA or Day of Post-Operative clinical visit (dCD). Neuropsychometric assessment at baseline, will allow screening for MCI and determining if there is a change in cognitive performance from recruitment to operative day due to statin alteration. The intention to treat principle will be used for all analyses. All of the analyses will be performed in two general ways. 1) Significant neurocognitive change for both CEA will be defined compared to an appropriate reference group frequency matched for age, education level, pIQ, and type of anesthetic or sedation. Significant eCD will be defined as performance: (1) $\geq 2SD$ worse than reference group in two or more cognitive domains or (2) $\geq 1.5SD$ worse than the reference group in all cognitive domains tested.

The following data will be kept for patients having CEA: demographic and risk factor variables (age, gender, race, a history of hypertension, diabetes, level of glycosylated hemoglobin, previous myocardial infarction, previous CEA, ApoE genotype, pre-morbid IQ, MCI), degree of carotid stenosis, all additional cerebrovascular workup (i.e. Intracranial MRA, SPECT scanning, angiography, etc.), previous surgeries/anesthetics, laboratory values, all standing medication names (statin usage), doses, and

durations, and all neurologic and neuropsychological scores. Data will also be kept on the results of the delirium screen and the post-operative pain scores.

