We anticipate that patients, who are on a sub-maximal statin regimen, will experience more eCD and dCD than patients on a pre-existing maximal statin regimen or randomized to a maximal statin regimen. We anticipate that patients who are randomized to atorvastatin 10mg will experience more eCD and dCD than patients randomized to atorvastatin 80mg. We anticipate that simvastatin will provide more neuroprotection than atorvastatin or rosuvastatin measured by lower incidences of eCD and dCD at comparable statin doses for lipid lowering. Conclusions regarding the arm of statin naïve patients may be somewhat underpowered depending on the number of statin naïve patients we see. Results will be interpreted with according caution. We expect the randomized nature of the trial to randomly distribute patients with regard to age, diabetes, educational level, pIQ, MCI, perioperative delirium and ApoE-e4, but now have accounted for these in the statistical plan and also include long-term outcomes out to a year as well. Post-hoc assessments will also examine whether the primary findings regarding eCD and dCD apply to subgroups of patients but these analyses will be viewed as hypothesis generating only.

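### Baseline MCI is both a ground for exclusion and a planned model term on the same MoCA/AD8 cut-offs, so the planned adjustment cannot be run if one rule serves both purposes

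*Combined protocol and SAP*

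**What the plan says.** Section 2.1.5 gives the two cut-offs: "we will screen patients for cognitive decline ($AD8 \geq 2$) and the MoCA (≤ 25) prior to randomization". Its closing sentence, which treats delirium in the same way, turns the result into an analysis variable: "MCI at study onset will be identified using the criteria outlined above, and these data will be analyzed in the univariate and multivariate models". Section 9.1 includes MCI in the risk-factor variables to be kept ("ApoE genotype, pre-morbid IQ, MCI"). Under Interpretation of Results it expects randomisation to "randomly distribute patients with regard to age, diabetes, educational level, pIQ, MCI, perioperative delirium" and ApoE-e4, and adds that the statistical plan accounts for these factors.

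Section 3 (Study Design) says: "Those with baseline MCI will be screened out from the study and not followed". Section 6.2.2 repeats this. Exclusion criterion 2 in Section 4.2 and the screen-failure lists in Sections 6.2.1 and 11.2 use the same two cut-offs, joined by AND. Sections 3 and 6.2.2 word the rule differently: "If both assessments are not within normal ranges, these patients will not be randomized or assigned to the observational arm". Section 4.3 requires patients to pass the screening tests, in the plural, before randomisation.

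**The concern.** Section 2.1.5 names MCI as a possible confounder of a cognitive-change endpoint and says that "the incidence of pre-operative MCI may be as high as 50% in our patient population". The authors answer this in two ways, by screening MCI out and by modelling it, and the two are incompatible if MCI means the same thing in both places. Patients who are screened out have no eCD or dCD outcome, so they cannot contribute to any model.

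Two things are at stake. The statement in Section 9.1 that MCI has been accounted for would not be delivered, which matters where randomisation does not protect the comparison. In addition, the screening rule decides who enters the trial, and ten listed sites would apply wording that supports two different rules.

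**Working it through.** There is no sample size, power or alpha figure to reproduce here. The check is one of logic and estimability.

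**Step 1. Cross the exclusion rule with the MCI definition.** Let AND mean both tests abnormal, and OR mean at least one abnormal.

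| Exclude if | MCI coded yes if | Enrolled patients abnormal on one test | MCI among enrolled |
|---|---|---|---|
| AND | AND | enter, coded no | all no |
| OR | OR | none | all no |
| OR | AND | none | all no |
| AND | OR | enter, coded yes | varies |

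In the two rows where the same rule is used for both purposes, MCI is constant. It varies only in the last row. There, patients coded as having MCI are enrolled, which contradicts the statement in Sections 3 and 6.2.2 that those with baseline MCI are screened out.

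**Step 2. Estimability.** A model with intercept, treatment and an MCI column of zeros has a design matrix of rank 2 for 3 parameters (checked with 675 rows, the size of Arm 2). The MCI coefficient cannot be estimated and the term drops out.

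**Step 3. Which comparisons are affected.**
- Arm 2 (338 v 337) and Arm 3 (50 v 50) are randomised. Losing a baseline covariate does not bias them.
- Objective 2 compares supplemented Arm 2 patients with the observational Arm 1: 338 + 225 = 563 patients, not allocated by chance.
- Objective 4 groups all patients by dose at surgery, so it mixes randomised and observational patients.

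**Step 4. The combination rule, side by side.**
- Sections 4.2, 6.2.1 and 11.2: MoCA abnormal AND AD8 abnormal.
- Sections 3 and 6.2.2: the wording can mean that both are abnormal, or that the two are not both normal (OR).
- The neighbouring laboratory screen shows that the conjunction cannot be relied on. CK and LFT elevations are joined by AND in Sections 6.2.1, 6.2.2 and 11.2, but by OR in Section 7.2.1.

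**Step 5. How far the two readings could differ (assumed rates; the documents give none).** Let m and a be the proportions abnormal on MoCA and AD8, and b the proportion abnormal on both. AND excludes b and OR excludes m + a − b. Under AND, the share of enrolled patients abnormal on one test is (m + a − 2b)/(1 − b).
- m = 0.5, a = 0.2, independent (b = 0.10): AND excludes 10% and OR excludes 60%. The single-abnormal share under AND is 0.50/0.90 = 56%.
- m = 0.5, a = 0.2, maximal overlap (b = 0.20): AND excludes 20% and OR excludes 50%. The share is 0.30/0.80 = 38%.
- Over m from 0.3 to 0.6, a from 0.1 to 0.3, and overlap from independent to maximal, the share runs from 0% to 66%.

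The range is too wide to be an estimate. It shows only that the choice of reading can matter a great deal.

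**The case against.** The strongest reply is that little harm follows. Section 9.1 adjusts for factors out of balance at p < 0.10; a constant term never meets that test and simply falls away. Section 2.1.5 also says that MCI's effect on postoperative cognitive dysfunction seems very small, and education and premorbid IQ remain among the baseline factors. This stands for the randomised contrasts. It is weaker elsewhere: the small effect is drawn from on-pump coronary surgery, and Section 2.1.5 commits to analysing MCI in the models nonetheless.

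A second reply is that MCI need not be empty. Section 2.1.5 does not spell out how the two cut-offs combine, and Section 9.1 mentions baseline neuropsychometric assessment as a further screen for MCI. However, Section 6.2.3 places that battery after randomisation and no MCI criterion is given for it, while Section 2.1.5 ties the analysed variable to the criteria it has just listed.

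A reader might infer more than the documents support:
- **That patients abnormal on one test certainly enter unflagged.** This follows only if AND is used both to exclude and to define MCI, and Sections 3 and 6.2.2 leave that open. Even then the MoCA and AD8 scores are collected; what is missing is a defined analysis variable. Inclusion criterion 6 (no cognitive impairment that would impede testing) and the exclusion of documented dementia also apply.
- **That enrolment would fall by up to half.** The projection of 210 a year in Section 9.2 already describes patients as eligible and enrolled, and enrolment follows the screen. An MCI frequency of up to 50% is not a screen-failure rate on these two tests.
- **That floor effects hide eCD in impaired patients.** The documents give no figure for this.

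**Conclusion.** The contradiction is in the text and should be corrected. If one MoCA/AD8 rule serves for both exclusion and covariate, MCI is constant among enrolled patients, apart from any eligibility deviations, and the planned adjustment cannot be run. The consequence is limited: no bias in the Arm 2 and Arm 3 randomised contrasts, but no planned MCI control in the non-randomised parts of Objectives 2 and 4.

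The screening rule is also stated inconsistently, so sites could enrol different populations. The documents do not settle which reading is intended. Under the AND reading, patients abnormal on one test enter with no analysis variable defined for them. Their number cannot be derived from the documents.

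**What to change.** 1. In Sections 2.1.5 and 9.1, replace the MCI yes/no term with the continuous baseline MoCA score and include it in the logistic models, in particular for Objectives 2 and 4. Carry this into Section 9.5, whose parallel list of risk factors omits MCI. Amend the sentence under Interpretation of Results to match.
2. Reconcile Sections 3, 4.2, 6.2.1, 6.2.2 and 11.2 to one unambiguous rule of the sponsor's choosing, stating whether one or two abnormal tests exclude. Align the statement that those with baseline MCI are screened out with that rule.

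The MoCA is given to all consented patients before randomisation or assignment to Arm 1, so no test, visit or patient is added; the cost is protocol and SAP wording. There is one limit. If either abnormal test excludes, enrolled scores run only from 26 to 30, so the term can be estimated but carries less information. A subgroup with MoCA 25 or below exists only if the AND rule is kept, and should be specified only in that case.
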